- v. After study completion, participants will participate in a phone interview, if they agree, to gather more information about their experience, using a standardized set of questions (see Supplemental Study Documents).
- w. Participants may be given the option to participate in future research studies.

Data collection for the Corrie Digital Health group and the historical standard of care comparison group to assess the primary outcome:

- a. Following study completion, we will submit requests to Johns Hopkins Hospital and Johns Hopkins Bayview Medical Center, Massachusetts General Hospital Partners group, and Reading Hospital administrative data managers to obtain the following data on both groups: age, sex, race, language, body mass index, marital status, smoking status, diagnosis of STEMI versus NSTEMI, insurance status (payor index), admission date, discharge date, type of intervention received in hospital (PCI or CABG), a discrete count of AHRQ identified Elixhauser comorbidities based on ICD-9-CM and ICD-10 diagnosis codes, discharge disposition, readmission, days to readmission, reason for readmission, ED visits, observation visits, and mortality.
- b. These variables will be obtained for both groups via the administrative databases to ensure standardization of variables and collection.
- c. For the historical control group we will query data for patients admitted to each hospital from October 1, 2015 to October 1, 2016 for a STEMI or NSTEMI. To obtain data for the Corrie Digital Health group, 30 days after the last enrolled participant is discharged from the hospital, we will send a list of

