Statistical plan including sample size justification and interim data analysis.	
Allowing for 10% of drop-outs during 30-day follow-up, the aim was to recruit N=200 in the intervention group and N=1,000 patients in the comparison group to provide around 90% power at the 2-sided 5% level of significance to detect a hazard ratio of 0.5 (ie, 50% reduction in a hazard of the intervention group), assuming 85% of patients in the comparison group survive or are not readmitted by the end of study (Stata stpower). The incident readmission rate of patients in our historical comparison group admitted to JHH and JHBMC was 16 cases per 100 person-months. We aim to detect a 50% risk reduction in readmission rates because our solution is comprehensive in nature and it is estimated that 76% of 30-day readmissions are potentially preventable using proven standards of care.
 
Our statistics will be primarily descriptive. We will examine characteristics of participants who join the study including demographics (e.g., age, sex, race/ethnicity, level of education, mHealth literacy, body mass index, marital status, occupation, annual income, insurance coverage) and clinical characteristics (e.g., severity of MI by TIMI/GRACE score, Killip Class, severity of cardiovascular disease by ejection fraction, medications, cardiac risk factor profile including dyslipidemia and lipid management characteristics as above), hypertension, diabetes, smoking, prior history of MI, and other comorbidities such as COPD, anxiety, and depression. We will examine primary and secondary outcomes as frequencies (percentage) for categorical variables and mean (SD) for continuous variables according to site of enrollment (JHH or JHBV) and type of mobile device (iPhone or Android). We will compare baseline characteristics of study participants using χ^2 and t-tests for categorical and continuous variables, as appropriate.
 
In assessing readmissions and cost-effectiveness, concurrent and historical controls will be matched to enrolled patients based on sociodemographic/clinical variables, and risk stratification using APR DRG / severity of illness scores (which are shown in the literature to be predictive for readmissions). We will conduct a Cox survival analysis to compare time to first readmission between the Corrie digital health group and the historical comparison group. We will build a Markov model of cost-effectiveness with the perspective of a hospital adopting Corrie technology, taking into account the lifelong outcome and cost of the Corrie discharge process versus the standard

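### The stated 90% power for a hazard ratio of 0.5 comes from an approximation that is optimistic at 1:5 allocation; simulated power is about 75–82% with 10% dropout and 80–84% without

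*Combined protocol and SAP*

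**What the plan says.** The only power statement is in section 7, Study Statistics, in the row on the statistical plan and sample size. Its elements are:

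- Sample size: "the aim was to recruit N=200 in the intervention group and N=1,000 patients in the comparison group".
- Dropout, already built into those numbers: "Allowing for 10% of drop-outs during 30-day follow-up".
- Claim: "to provide around 90% power at the 2-sided 5% level of significance to detect a hazard ratio of 0.5".
- Comparison-group assumption and software: "assuming 85% of patients in the comparison group survive or are not readmitted by the end of study (Stata stpower").
- Observed rate offered in support: "The incident readmission rate of patients in our historical comparison group admitted to JHH and JHBMC was 16 cases per 100 person-months".

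The same row plans a Cox analysis of time to first readmission, the primary outcome. It does not say which stpower method was used, and it reports no check of the approximation at this allocation. It also says that, for readmissions, "concurrent and historical controls will be matched to enrolled patients", but the power statement makes no reference to matching.

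**The concern.** Formulas that convert a total number of events into power assume how those events divide between the arms. Schoenfeld's uses the allocation ratio, which is right when the hazards are equal. Here one patient in six is in the Corrie arm, and that arm is also assumed to have half the hazard. The smaller arm therefore supplies far fewer events than its share of patients, and that small count limits the precision of the hazard ratio. The formula then overstates power.

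This is the plan's only power figure and it concerns the primary outcome. If the result is not significant, a reader told that power was 90% would take it as stronger evidence against a halving of the hazard than the design can give.

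**Working it through.** **Inputs (all from section 7).** Hazard ratio 0.5; 2-sided 5% test; comparison group 85% event-free at 30 days; 200 v 1,000 patients; 10% dropout, so 180 v 900 if dropouts contribute nothing. The observed rate of 16 per 100 person-months gives exp(−0.16) = 0.852 event-free, which agrees with 85%.

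**1. Expected events at HR 0.5.** Corrie event risk = 1 − 0.85^0.5 = 0.078.

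- 180 v 900: 180 × 0.078 = 14.0 and 900 × 0.15 = 135.0; total 149.0.
- 200 v 1,000: 15.6 and 150.0; total 165.6.

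**2. Reproducing the stated figure.** Schoenfeld power = Φ(ln 2 × √(E × 1/6 × 5/6) − 1.96), where E is total events.

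- E = 149.0 (180 v 900): 88.4%.
- E = 162 (1,080 × 0.15, taking 15% as the overall event probability): 90.8%.
- E = 165.6 (200 v 1,000, no dropout): 91.4%.

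So about 90% is what this formula returns.

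**3. Why it is too high.** The formula implies 149/6 = 24.8 Corrie events; 14.0 are expected. Its standard error for the log hazard ratio is 1/√(149.0 × 5/36) = 0.220, whereas the expected counts give √(1/14.0 + 1/135.0) = 0.281. Other closed forms on the same inputs are much lower, for 180 v 900 and 200 v 1,000 respectively: Freedman 69.9% and 74.4%; Wald with arm-specific variances 69.6% and 74.1%; two proportions 76.4% and 81.3%. The closed forms disagree this widely because of the allocation, so simulation is needed to settle the figure.

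**4. Simulation.** Exponential event times censored at day 30; 20,000 replicates; 2-sided 5% test, counting only rejections in favour of Corrie; Monte Carlo standard error about 0.3 points. Unmatched and unadjusted, HR 0.5:

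| Scenario | Log-rank | Cox Wald | Cox likelihood ratio |
|---|---|---|---|
| 180 v 900 (dropouts contribute nothing) | 76.4% | 75.6% | 80.0% |
| 180 v 1,000 (Corrie arm only loses 10%) | 77.6% | 76.7% | 81.0% |
| 200 v 1,000, 10% dropout spread over 30 days | 79.1% | 78.5% | 82.3% |
| 200 v 1,000, no dropout | 81.5% | 80.8% | 84.4% |

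Separately written code with 10,000 replicates agreed within one point in every cell. At HR 1 with 200 v 1,000, rejection in the beneficial tail was 2.2%, 2.0% and 2.6% (nominal 2.5%), so the lower power is not explained by a badly undersized test.

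**5. Sensitivity to the comparison-group rate.** With 85.2% event-free: 76.0/75.2/79.5% at 180 v 900 and 80.6/79.9/83.3% with no dropout. With 84% event-free (reading 16 per 100 as a 16% risk; 10,000 replicates): 78.7–82.5% at 180 v 900 and 83.0–86.1% with no dropout. None reaches 90%.

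**6. Where 90% is reached** (10,000 replicates; log-rank/Wald/likelihood ratio):

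- 180 v 900: HR 0.42 gives 90.5/90.0/92.2%; HR 0.44 gives 88.1/87.5/90.0%.
- Dropout spread over 30 days: HR 0.43 gives 90.7/90.4/92.4%; HR 0.45 gives 88.0/87.4/90.3%.
- No dropout: HR 0.45 gives 90.0/89.6/91.8%.

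**The case against.** The strongest reply is that the plan made no error against its own method. Schoenfeld is a standard formula, the planned analysis is a Cox model, and the formula gives the stated figure. Of the closed forms compared in step 3 it is the one that lands near 90%, so a careful reader could infer which was used. That is true, and it rules out calling this a miscalculation. It does not give the design the power claimed: the formula is an approximation, and on these inputs it fails in the favourable direction.

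Second, the simulated figure ignores matching too, so it is not the power of the planned matched analysis either. This stands, and the restated sentence should say so. It does not rescue the 90%, which ignores matching in the same way.

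Third, little can now change. The sample-size text is in the past tense, and section 4 already gives a fixed count of 541 ineligible or declining patients, so recruitment may be well advanced; a null result is better read from its confidence interval. This limits the consequence to reporting, but a published power figure will still be read alongside the result.

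Finally, section 4 says of the outcome data: "These variables will be obtained for both groups via the administrative databases to ensure standardization of variables and collection". Total loss of 10% in both arms may therefore be pessimistic. That is why the lighter-dropout and no-dropout cases are shown; they fall short as well.

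**Conclusion.** The concern holds. On the plan's inputs, power for a hazard ratio of 0.5 is about 75–82% with 10% dropout and about 80–84% with none. The lower bound of 75% allows for Monte Carlo error and for the 85.2% event-free input; at exactly 85% the lowest simulated value is 75.6%. Against 90%, the overstatement is about 8–15 points with dropout and 6–9 points without. The corresponding risk of missing a true halving is about 18–25% and 16–19%, rather than 10%.

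This rests on proportional exponential hazards, censoring at day 30, and an unmatched, unadjusted comparison. Power after matching or covariate adjustment was not examined. Severity: should be fixed. The stated figure is wrong for this design on every dropout reading, but the remedy is confined to how power is reported.

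**What to change.** In section 7, name the stpower method that was used and replace the power sentence with wording such as:

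> With 200 Corrie and 1,000 comparison patients, about 85% of comparison patients event-free at 30 days and a 2-sided 5% test, simulated power for a hazard ratio of 0.5 in the unmatched, unadjusted comparison is about 75–82% with 10% dropout, depending on the test and the timing of dropout, and about 80–84% with no dropout. Power of 90% applies at a hazard ratio of about 0.42–0.44 with 180 v 900 evaluable patients, and about 0.45 with no dropout. These figures do not describe the matched analysis.

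The cost is a short rewording and a less favourable stated power. No extra patients are needed, and enrolment, design and analysis do not change.

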	
participant identifiers to the hospital data managers.
 
d. In an ancillary study restricted to both groups of Hopkins participants, we will perform an Epic data extraction focused on measures of 2018 AHA/ACC guideline-directed cholesterol management such as serum lipid values upon admission through 12 months of hospital discharge, whether patients were on lipid lowering therapy at the time of admission, prescription of lipid lowering therapies at the time of discharge including statins and non-statins, whether the statin was a high intensity statin regimen at the time of hospital discharge, if patients were not on statin therapy due to a history of side effects, very high risk vs not very high risk status, and whether additional lipid lowering therapies were prescribed within 12 months of hospital discharge.
 
Data collection for patients who were deemed ineligible/declined to participate in the Corrie Digital Health group to assess selection bias:
 
a. Following study completion, we will submit requests to Johns Hopkins Hospital and Johns Hopkins Bayview Medical Center administrative data managers to obtain the following data on the 541 patient who were deemed ineligible/declined to participate in the Corrie intervention group: age, sex, race, marital status, smoking status, diagnosis of STEMI versus NSTEMI, insurance status (payor index), readmission, days to readmission, and reason for readmission.
 
b. These variables will be obtained via the administrative databases to ensure standardization of variables and collection to those who were enrolled in the Corrie intervention group.

--	--

MiCORE Reading Hospital cohort:

Reading Hospital is participating in this study through a grant from the Reading Hospital Foundation. The participation of patients recruited from Reading will be limited to the 30-day (approximate) initial enrollment period. The data collected from this cohort will be used to support the study’s primary outcome: 30-day readmission rate.

Study procedures for Reading Hospital	
Study design	Same as for primary cohort

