Study duration	Each participant will join the study for the entirety of their hospitalization following enrollment. This inpatient phase will last approximately 1 to 5 days, depending on the length of stay and the enrollment date, with the goal being to enroll the patient participant as early as possible in his/her hospitalization. Then enrollment will continue for 30 days following discharge for an approximate study duration of 30 to 40 days.
Routine care	Same as for primary cohort
Treatment failure or participant removal criteria	None (same as for primary cohort)
Participants receiving therapy when study ends or if a participant’s participation in the study ends prematurely	Same as for primary cohort
Procedural steps	Same as for the Corrie Digital Health group in the primary cohort, paragraphs a through n, and r through w. The Reading cohort will not participate in the procedural steps for the 6 and 12-month follow-ups, as described in paragraphs p and q.

	Data collection for the Corrie Digital Health group and the historical standard of care comparison group to assess the primary outcome will be the same.
--	--

5. Inclusion/Exclusion Criteria

a) The Corrie Digital Health group

Inclusion Criteria	Exclusion Criteria
-Patient admitted for acute myocardial infarction; MI present at the time of admission and Type I NSTEMI or STEMI -18 years or older - smartphone ownership	-Non-English speaking -Visual, hearing, or motor impairment which precludes use of the intervention -Persons not able to participate on due to severity of illness (e.g., intubated and on sedation in the setting of cardiogenic shock)

b) The Historical Comparison group

Inclusion Criteria	Exclusion Criteria
-Patient admitted for acute myocardial infarction; MI present at the time of admission and NSTEMI or STEMI -18 years or older	-Non-English speaking

6. Drugs/ Substances/ Devices

- a. The rationale for choosing the drug and dose or for choosing the device to be used.
- b. Justification and safety information if FDA approved drugs will be administered for non-FDA approved indications or if doses or routes of administration or participant populations are changed.
- c. Justification and safety information if non-FDA approved drugs without an IND will be administered.

Devices: Smartphone + Apple Watch + Silicone HealthBand + iHealth BP monitor +/- Apple TV

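### The severity score planned for matching is not in the data request, and the primary Cox analysis does not say whether it uses the matched set, covariates or hospital

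*Combined protocol and SAP*

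**What the plan says.** **Matching and model.** Section 7 (Study Statistics, statistical plan) says that, for readmissions and cost-effectiveness, "concurrent and historical controls will be matched to enrolled patients based on sociodemographic/clinical variables, and risk stratification using APR DRG" and severity of illness scores. It gives no variable list, ratio or method. The next sentence is the primary analysis: "We will conduct a Cox survival analysis to compare time to first readmission between the Corrie digital health group and the historical comparison group". It names no covariate, stratum or matched set.

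**Data request.** Under Section 4, data collection, item a, requests go to the two Johns Hopkins hospitals and to "Massachusetts General Hospital Partners group, and Reading Hospital administrative data managers to obtain the following data on both groups". The list covers demographics, payor, smoking, body mass index, infarct type, in-hospital procedure, disposition, outcomes and "a discrete count of AHRQ identified Elixhauser comorbidities based on ICD-9-CM and ICD-10 diagnosis codes". It has no APR DRG or severity of illness score. Item c takes as historical controls "patients admitted to each hospital from October 1, 2015 to October 1, 2016".

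**Eligibility.** Section 5 limits the app group to "Type I NSTEMI or STEMI -18 years or older - smartphone ownership". It excludes "Persons not able to participate on due to severity of illness" and people whose sight, hearing or motor impairment prevents use of the app. The historical group has none of these limits; its infarct criterion does not specify Type I.

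**Selection bias.** Section 4 also requests data, from the two Hopkins hospitals only, on 541 patients "deemed ineligible/declined to participate in the Corrie Digital Health group to assess selection bias".

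**The concern.** Without randomisation, the hazard ratio can be read as an app effect only if differences in patient risk are dealt with. Here the groups differ by calendar period and by entry criteria. Section 7 itself describes severity scores as predictive of readmission, yet that score is the one named matching input that will not be available.

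The second problem is the open choice of analysis. The text allows an unadjusted Cox model on everyone, an adjusted one, or a Cox model on a matched set of unstated ratio. These can give different estimates and very different power, and nothing stops the choice from being made after results are seen. Hospital is not named in the matching rule or the model, although patients come from several hospitals and nothing makes the hospital mix alike in the two groups.

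**Working it through.** **1. Matching inputs against requested fields**

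| Needed for | Requested for both groups (Section 4, item a)? |
|---|---|
| Sociodemographic matching | Yes: age, sex, race, marital status, payor |
| Clinical matching | Largely: STEMI/NSTEMI, PCI/CABG, Elixhauser count, smoking, BMI |
| APR DRG / severity of illness score | No |
| Hospital | Not listed, but known from whichever data manager supplies the record |
| Smartphone ownership, Type I status, impairment, inability to take part | No |

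The Elixhauser count is a comorbidity count, not the severity score. TIMI/GRACE, Killip class and ejection fraction appear in Section 7 only to describe people who join the study.

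**2. The plan's own power figure**

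Inputs from Section 7: 200 v 1,000; 10% dropout, hence 180 v 900; control event-free proportion 0.85; hazard ratio 0.5; two-sided 5%; power of around 90%.

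- App-group risk: 1 − 0.85^0.5 = 0.078.
- Events: 180 × 0.078 + 900 × 0.15 = 14.0 + 135 = 149.
- Schoenfeld, with a the app-group share: power = Φ(√(E·a(1−a))·|ln HR| − 1.96).
- With a = 1/6: √(149 × 5/36) × 0.693 − 1.96 = 1.19, so power is 88.4%. Without dropout (166 events) it is 91.4%.

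The stated figure therefore reproduces, for the full, unmatched, unadjusted comparison.

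**3. If the Cox model used a 1:k matched set**

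The ratio is not in the documents, so the range is an assumption. All 200 app patients are taken as matched, with 10% dropout. Events = 14.0 + 180k × 0.15, and a = 1/(1+k).

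| Ratio | Events | Power |
|---|---|---|
| 1:1 | 41 | 60.3% |
| 1:2 | 68 | 76.9% |
| 1:3 | 95 | 83.3% |
| 1:4 | 122 | 86.5% |
| 1:5 | 149 | 88.4% |

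At 1:5 the matched set needs 5 × 200 = 1,000 controls, the whole planned comparison group. With a pool of that size, matching would leave nobody out.

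**4. If all patients are kept and covariates are added**

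Let R² be the share of variation in group membership explained by the covariates (assumed). Replacing E by E(1−R²) gives 86.7%, 84.9%, 80.5% and 75.1% at R² = 0.05, 0.10, 0.20 and 0.30.

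Schoenfeld is optimistic at this 1:5 split with few app-group events. Simulation (exponential times, censoring at 30 days) gives about 77% unadjusted. A Cox model with group and one covariate gives about 72 to 74% at R² = 0.10 and 68% at 0.20. With 13 non-prognostic covariates and four hospital strata, at R² = 0.10 for one covariate, power is about 71% with equal hospital mix. It is about 61% with an assumed very uneven mix (app 45/45/5/5, historical 20/10/40/30).

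**5. Room for covariates**

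Take age, sex, STEMI/NSTEMI and Elixhauser count at one term each, and race, payor and procedure at an assumed three levels each: 4 + 6 = 10 terms. Severity as one ordered term and group make 12. Then 149/12 = 12.4 events per term. Hospital strata use no term but do cost precision, as step 4 shows.

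**The case against.** The best defence is that the plan does foresee confounding. It intends to match when assessing readmissions, and the Cox sentence on readmission follows at once, so the natural reading links the two. Most likely matching variables are requested, and infarct type, procedure and Elixhauser count carry part of the severity information. Hospital is known from the data source, and Section 7 already tabulates outcomes by the two Hopkins sites. The statistics are described as mainly descriptive, and Section 4 plans to look at selection bias.

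Much of this stands, and it limits the point. A reader might infer that the matching as a whole cannot be run. The documents do not support that: only the severity part lacks its input. A reader might also infer that the primary analysis is definitely unadjusted, or that severity and hospital go wholly uncontrolled. The text is ambiguous on the first, and partial risk measures are available for severity. Hospital is an unstated specification, not a missing field. The device-loan programme may also soften the smartphone criterion.

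What does not stand is that the intention is enough. The same section sets a two-sided test with a power target for this comparison, so it is not merely descriptive. The Cox sentence and the sample size both refer to the whole historical group. The 541-patient request measures selection at two hospitals but adjusts nothing.

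**Conclusion.** The point holds as a fault in specification and should be corrected. The severity stratification cannot be carried out with the data requested. Whether the primary Cox model is matched, adjusted or stratified by hospital is left open. *Concurrent* controls have no definition, and the objective and the Cox sentence name only a historical group.

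The firm number is the effect on power: 88% belongs to the full set or to 1:5 matching, against about 60% at 1:1 and 77% at 1:2, assuming every app patient is matched. The stated power is not wrong for the unmatched design.

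The size of the confounding cannot be given. The documents report neither severity by group nor readmission rates by hospital, so the direction of any hospital effect is unknown. A reader might want to size the fault from the one-sided eligibility criteria. If 10, 20 or 30% of historical patients would have been excluded from the app group, at 1.25, 1.5 or 2 times the risk (all assumed), p = 0.15/((1−s) + sR) and HR = ln(1−p)/ln(0.85). A useless app would then show a hazard ratio of about 0.97, 0.90 or 0.75. That is residual eligibility bias in an unadjusted, unmatched comparison. The change below does not remove it, and it does not measure the harm from the missing score or model terms.

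**What to change.** 1. Add the APR DRG severity of illness field to the request for both groups and use it in the primary analysis. If it cannot be obtained, say that Elixhauser count, STEMI/NSTEMI and PCI/CABG serve as partial substitutes.
2. State one primary analysis before the linked outcome data are requested: a Cox model of the app group against all historical patients, stratified by hospital. Adjust it for a short fixed list of pre-discharge variables (for example age, sex, race, payor, STEMI/NSTEMI, PCI/CABG and Elixhauser count) plus severity. Keep matching as a sensitivity analysis, within hospital, with the ratio stated. If the sponsor prefers matching as primary, match within hospital, state the ratio, say that the Cox model uses the matched set, and restate the power.
3. Define *concurrent* or delete it.
4. State that confounding from smartphone ownership, Type I status, impairment and inability to take part remains. Use the 541-patient data to gauge it at the two Hopkins hospitals.
5. Report patients and events by hospital and group. The request names four of the six design hospitals, and a hospital with only one group adds nothing to a stratified contrast.

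**Cost.** Wording, at most one administrative field, and some power: to about 85% at R² = 0.10 and 81% at 0.20 by Schoenfeld, lower by simulation, and lower again if hospital mix differs strongly. With about 149 events, only about 14 of them in the app group at the planned effect, the list should stay short. The exact variables and coding are the sponsor's choice, provided they are fixed in advance. Section 7 already quotes a historical readmission rate for the two Hopkins hospitals, so some control outcomes have been seen. That is one more reason to fix the model now.
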